### 9.2.2 Clinical Status

The 8-point ordinal scale will be summarized descriptively by treatment group and study day. The last known clinical status will be used for days with missing clinical status. All post-baseline days with missing ordinal scale score will use the previous last known clinical status.

Additionally, stacked bar charts will be presented for the proportion of subjects in each category by group and study day.

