9.4.5. Secondary Endpoints (Efficacy)

The proportion of subjects alive and discharged from the ICU at Day 14 and Day 28 and the proportion alive and free of respiratory failure at Day 60 and will be presented and analyzed as described for the primary efficacy endpoint. Subjects who discontinue from the study prior to each study day will be considered treatment failures.

Clinical Status will be assessed using a generalized linear mixed model, assuming a multinomial distribution. The model will include the Day 1 value as a covariate with fixed effects of group,

study day and group-by-study day interaction and subject as a random effect. If the group-by-study day interaction is found to be statistically significant then comparisons between groups at Day 7, Day 14 and Day 28 will be obtained from this model. Additionally, stacked bar charts will be presented for the proportion of subjects in each category by group and study day.

For the time from randomization to first occurrence of respiratory failure or death on study due to any cause, the Kaplan-Meier method will be applied. Subjects will be censored at the time of last follow-up. For each group, the 25th percentile, median and 75th percentile will be presented, if possible. Possible differences between groups will be assessed by the log-rank test.

The total number of deaths per group will be presented for All-cause mortality at Day 90.

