#### **2.2.2 Secondary Endpoints**

- Types, frequencies, and severities of AEs and the relationships of AEs to IP; includes serious adverse events SAEs
- Proportion of subjects alive and free of respiratory failure at Day 60
- Change in clinical status (on a 0-8-point ordinal scale) of subject at Day 7, Day 14, and Day 28
- Proportion of subjects alive and discharged from ICU at Days 14 and 28
- Time from randomization to first occurrence of respiratory failure or death on study due to any cause up to Day 28
- Percent change from baseline in CRP at Days 3, 5, 7, 10, 14, 28
- Relative change from baseline in oxygenation index (PaO2/FiO2) up to Day 5

- All-cause mortality at Day 60 and Day 90
- Number of days alive and free of respiratory failure at Day 28
- Number of days with respiratory failure up to Day 28
- Number of days hospitalized up to Day 28
- Number of days in ICU (length of stay) up to Day 90
- Number of days alive outside of hospital up to Day 28
- Number of days alive outside of hospital up to Day 90
- To assess the pharmacokinetic profile in the study population

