### 7.3 Missing or Incomplete Data

Subjects who are randomized to the study and discontinue before the end of the study will not be replaced. Missing values will not be imputed unless otherwise specified.

For success/failure endpoints, subjects who discontinue prior to the specified time point will be included in the analysis as treatment failures and censored at the last day of follow-up for the time-to-event analysis.

For all other endpoints, the mixed effect model repeat measurement (MMRM) analysis will be employed. The MMRM analysis only includes the available data. It has been demonstrated that the MMRM approach leads to estimators with comparatively small bias, and controls Type I error rates at a nominal level in the presence of missing completely at random (MCAR) or missing at random (MAR) and some possibility of missing not at random (MNAR) data (see <https://pubmed.ncbi.nlm.nih.gov/19212876/>).

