### 9.2.3 Continuous Endpoints

For the following continuous endpoints, descriptive statistics will be presented by treatment group and study day. The changes or percent changes from baseline to each subsequent day will be calculated for each subject and descriptive statistics will be presented. Treatment differences between groups will be assessed using a mixed-effects model for repeat measures (MMRM). The model will include group, study day as fixed effects, baseline value as a covariate, interaction between study day and group, interaction between study day and baseline, and subject as a random effect.

- Percent change from baseline in C-reactive protein (CRP) at Days 3, 5, 7, 10, 14, 28
- Relative change from baseline in oxygenation index (PaO2/FiO2) up to Day 5

For each “number of days” endpoint listed below, descriptive statistics will be presented by treatment group. Treatment differences between groups will be assessed using analysis of variance (ANOVA) model with group as a fixed effect.

- Number of days alive and free of respiratory failure at Day 28

- Number of days with respiratory failure up to Day 28
- Number of days hospitalized up to Day 28
- Number of days in intensive care unit (ICU) (length of stay) up to Day 90
- Number of days alive outside of hospital up to Day 28
- Number of days alive outside of hospital up to Day 90

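### SAP 9.2.2 states no between-group comparison for the ordinal clinical status endpoint, and the protocol's Day 7, 14 and 28 comparisons hang on a significant interaction

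*SAP*

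**What the plan says.** SAP 2.2.2 lists among the secondary endpoints "Change in clinical status (on a 0-8-point ordinal scale) of subject at Day 7, Day 14, and Day 28". The analysis section, SAP 9.2.2, has three parts:

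- A summary: "The 8-point ordinal scale will be summarized descriptively by treatment group and study day".
- A missing-data rule: "The last known clinical status will be used for days with missing clinical status".
- A display: "Additionally, stacked bar charts will be presented for the proportion of subjects in each category by group and study day".

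It does not single out Days 7, 14 and 28 or define the change. A general sentence in SAP 7.3, placed after the rules for success/failure endpoints, reads: "For all other endpoints, the mixed effect model repeat measurement (MMRM) analysis will be employed".

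Protocol 9.4.5 (V4.0) is different. There, "Clinical Status will be assessed using a generalized linear mixed model, assuming a multinomial distribution", with the Day 1 value as covariate, fixed effects for group, study day and their interaction, and a random subject effect. It continues: "If the group-by-study day interaction is found to be statistically significant then comparisons between groups" at Days 7, 14 and 28 will be taken from the model. SAP 1.0 states that its analyses take precedence over the protocol's, and gives its basis as protocol V5.0.

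**The concern.** A listed secondary efficacy endpoint has no stated comparison between arms in the document that governs the analysis. The SAP gives no reason, so the gap cannot be read as a deliberate choice. An analyst who wants an effect estimate would have to choose the method, the days and the handling of deaths without a prespecified rule.

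Going back to the protocol text would not fully repair this. The endpoint is defined at three days, yet the protocol produces comparisons at those days only after a significant interaction. A treatment that helps equally at all three days has no interaction to find. The protocol also does not say that the overall group effect is the result to be reported.

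**Working it through.** **Step 1. Compare the SAP sections.**

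| SAP section | Endpoints | Between-group analysis named |
|---|---|---|
| 9.2.1 | Day 60 responder status, ICU discharge, mortality | Logit model as for the primary |
| 9.2.2 | Clinical status | None |
| 9.2.3 | CRP, PaO2/FiO2 | MMRM |
| 9.2.3 | Day counts | ANOVA |
| 9.2.4 | Time to respiratory failure or death | Log-rank |
| 9.3 | Exploratory laboratory markers | MMRM |

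Only 9.2.2 is empty.

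**Step 2. Does SAP 7.3 fill the gap?** Read literally, its MMRM sentence reaches clinical status. But 7.3 says MMRM uses available data only, whereas 9.2.2 carries values forward. The MMRM endpoints in 9.2.3 and 9.3 are all continuous measures and do not include this score. MMRM would also treat 0 to 8 as an interval scale, with death one unit worse than 7. The two sections conflict, and 7.3 does not supply a usable model.

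**Step 3. How often does the protocol's gate open?** The documents give no power figure for this endpoint. Their one power statement is for the primary. It reproduces with d = 0.957 − 0.70 = 0.257: an uncorrected n′ of 32.6 per group gives 80.0% power, and the continuity-corrected size is (n′/4)[1 + √(1 + 4/(n′d))]² = 8.15 × 4.91 = 40.0. It does not bear on clinical status.

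For the gate, write the cumulative-logit form (an assumption; the protocol says multinomial without naming a link):

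logit P(Y_it > k) = −c_k + γ·base_i + δ_t − (β + θ_t)·group_i + u_i

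A benefit constant over days means every θ_t = 0. The interaction null is then true, so its test rejects with probability α = 0.05 (Protocol 9.1) whatever the size of β.

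**Step 4. Simulation check.** All inputs are assumptions: 40 per arm, Days 7, 14 and 28, five collapsed categories, a binary baseline covariate, a constant conditional odds ratio, likelihood-ratio tests at 0.05, and 200 to 300 runs per setting. Two values in a cell are two separate sets of runs.

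| Random-intercept SD | Conditional OR | Interaction significant | Group term significant |
|---|---|---|---|
| 1 | 1 | 5.0% | 5.0% |
| 1 | 2 | 4.5% | 53.5% |
| 1 | 4 | 6.0% | 98.0% |
| 2 | 1 | 5.0%, 6.5% | 4.7%, 4.0% |
| 2 | 2 | 5.7%, 7.0% | 25.0%, 20.5% |
| 2 | 4 | 5.3%, 7.5% | 68.3%, 71.0% |
| 2 | 6 | 7.3% | 87.7% |
| 3 | 1 | 5.5% | 6.5% |
| 3 | 2 | 5.5% | 19.5% |
| 3 | 4 | 5.5% | 43.0% |

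The Monte Carlo standard error at 5% is √(0.05 × 0.95/200) = 1.5 points for 200 runs and 1.3 points for 300. Every interaction rate is within two standard errors of 5%, and there is no marked trend with the odds ratio. Some fits at SD 1, OR 4 gave numerical warnings, so treat the 98% as approximate.

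**Step 5. Are there Day 28 scores to analyse?** The Schedule of Assessments places clinical status at screening, on Day 1, daily in hospital and at discharge or early termination, but not at the Day 28 outpatient visit. Protocol 8.2.5 omits it too, though it collects survival. For anyone discharged earlier, the Day 28 score is the discharge score carried forward. Nothing in 9.2.2 says that a death after discharge replaces it.

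**The case against.** A reader might infer that a steady benefit would go untested under both documents. The protocol does not support that. Its model has group as a fixed effect, and that term is what captures a constant benefit; the interaction gates only the comparisons at individual days. In Step 4 the group term detects conditional odds ratios of 2 to 4 in about 20% to 98% of runs. What remains is that Protocol 9.4.5 does not name the group effect as the reported test.

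A reader might also infer that the SAP rules out any inference on this endpoint. That goes too far, because the sentence in 7.3 literally covers it. The SAP contradicts itself; it is not simply silent.

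Three further points are fair:

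- SAP analyses override the protocol, and the SAP rests on V5.0 while the supplied protocol is V4.0. Whether V5.0 kept the model or its gate cannot be checked, so the protocol part matters mainly as a warning against copying that text back.
- Descriptive reporting of a secondary endpoint can be defended in Phase 2. Here it is unexplained, and even the exploratory markers get a comparison.
- The SAP does compare other outcomes finer than the binary primary, such as day counts and time to respiratory failure or death. The documents do not show that this endpoint is the most informative one, and the point does not need it to be.

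The objection that a Day 28 odds ratio would put a confidence interval around carried-forward scores stands, and the fix takes it up.

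**Conclusion.** The point holds in this form: SAP 9.2.2 states no model, test, estimate or interval for a listed secondary efficacy endpoint, and SAP 7.3 conflicts with it without offering a suitable method. This rests on the SAP text alone and does not depend on the protocol version.

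Under Protocol V4.0, a benefit constant on the log-odds scale would yield the three day-specific comparisons in about 5% of trials (4.5% to 7.5% across the simulated settings). The nominal 5% follows from the test's level and depends little on the assumed inputs. The power values for the group term depend heavily on them and are illustrative only.

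The change should be made, but the primary analysis is unaffected.

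**What to change.** In SAP 9.2.2:

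- Specify a proportional-odds (cumulative logit) analysis with group and baseline score. Report the common odds ratio and 95% CI at Days 7, 14 and 28, with no interaction condition. Baseline adjustment then defines the change.
- Name one main comparison: either an overall group effect or one of the three days.
- Exempt this endpoint from the MMRM sentence in 7.3.
- Score deaths as 8 from the survival data, overriding any carried-forward value.
- State that Day 28 results after discharge rest on carried-forward scores, and present Day 14 or a sensitivity analysis alongside. Day 14 is affected in the same way for subjects already discharged, but over a shorter gap.

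If the current protocol still contains the gate, align its text.

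The cost is SAP text and a little programming, with no new data collection. The drawbacks are reliance on proportional odds and sparse categories in 80 subjects, so a collapsing rule should be fixed before unblinding.

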### 9.2.3 Continuous Endpoints

For the following continuous endpoints, descriptive statistics will be presented by treatment group and study day. The changes or percent changes from baseline to each subsequent day will be calculated for each subject and descriptive statistics will be presented. Treatment differences between groups will be assessed using a mixed-effects model for repeat measures (MMRM). The model will include group, study day as fixed effects, baseline value as a covariate, interaction between study day and group, interaction between study day and baseline, and subject as a random effect.

- Percent change from baseline in C-reactive protein (CRP) at Days 3, 5, 7, 10, 14, 28
- Relative change from baseline in oxygenation index (PaO2/FiO2) up to Day 5

For each “number of days” endpoint listed below, descriptive statistics will be presented by treatment group. Treatment differences between groups will be assessed using analysis of variance (ANOVA) model with group as a fixed effect.

- Number of days alive and free of respiratory failure at Day 28

- Number of days with respiratory failure up to Day 28
- Number of days hospitalized up to Day 28
- Number of days in intensive care unit (ICU) (length of stay) up to Day 90
- Number of days alive outside of hospital up to Day 28
- Number of days alive outside of hospital up to Day 90

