9. STATISTICS

9.1. Statistical Considerations

All tests of significance will be assessed at alpha level=0.05, 2-sided. All analyses and data presentations will be generated using SAS version 9.4, or higher (Cary, NC).

Subjects who are randomized to the study and discontinue before the end of the study will not be replaced. Missing values will not be imputed. For success/failure endpoints, subjects who discontinue prior to the specified time point will be included in the analysis as treatment failures and censored at the last day of follow-up for the time-to-event analysis. For all other endpoints, the mixed effect model repeat measurement (MMRM) analysis will be employed. The MMRM analysis only includes the available data. It has been demonstrated that the MMRM approach leads to estimators with comparatively small bias, and controls Type I error rates at a nominal level in the presence of missing completely at random (MCAR) or missing at random (MAR) and some possibility of missing not at random (MNAR) data (see <https://pubmed.ncbi.nlm.nih.gov/19212876/>).

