9.4.6. Exploratory Endpoints

For all other efficacy endpoints, descriptive statistics (number of subjects, mean, standard deviation, minimum, median and maximum values) will be presented by group and study day. The changes or percent changes from Day 1 to each subsequent day will be calculated for each subject and descriptive statistics will be presented. Possible differences between groups will be assessed using a MMRM analysis of variance\covariance. The model will include fixed effects of group, study day and group-by-study day interaction with subject as a random effect. The Day 1 value will be included when appropriate.

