## 3.0 STUDY DESIGN

This is a Phase 2, randomized, double-blind, placebo-controlled, 2-arm multicenter study to assess the safety and efficacy of oral STI-5656 (or placebo) in the setting of current SOC in subjects with RT-PCR confirmed SARS-CoV-2 infection and COVID-19 pneumonia (documented radiographically) requiring hospitalization. Subjects must have oxygen saturation levels <94% on room air or subject requires supplemental oxygen.

Eighty (80) subjects meeting eligibility criteria will be randomized at a 1:1 ratio to one of two treatment arms in addition to SOC treatments:

- Arm 1: STI-5656
- Arm 2: Placebo

The STI-5656 dose is 100 mg p.o. QD administered up to 14 days or until hospital discharge if sooner.

Details of the study conduct, visit schedule and assessments are described in the protocol. The Schedule of Assessments is referenced in Appendix 1.

An independent data monitoring committee (DMC) is established to evaluate the safety data from the study to ensure the ongoing safety of the study subjects and make recommendations to the Sponsor concerning safety and trial conduct (please refer to the DMC charter for details). An unblinded independent statistician will be used to facilitate DMC support.

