## **5.0 SAMPLE SIZE CONSIDERATIONS**

An evaluable sample size of 40 subjects per group will provide 80% power (alpha=0.05, 2-sided) to detect a difference between groups in the number of subjects alive and free of respiratory failure at Day 28. This assumes that 95.7% of subjects who received STI-5656 plus SOC and 70% of subjects who received placebo plus SOC only will be alive and free of respiratory failure at Day 28. This represents a treatment effect difference of approximately 26%.

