### 7.4 Interim Analysis

A non-binding interim futility analysis will be performed after 40 subjects have reached the study primary endpoint. The analysis will be performed by an independent biostatistician who will have no contact with the study team.

This interim analysis will use non-binding futility boundaries. At 50% planned subjects (40 subjects out of 80 subjects total), futility interim will be performed. O'Brien-Fleming beta spending function will be used. Futility bound on Z scale is 0.537. The futility bound is crossed if an observed Z statistic is less than 0.537. Nominal beta is 0.296 with cumulative beta being 0.065 at the interim and 0.192 at the final analysis. The above interim planning was performed under 1-sided test setting using nQuery Version 8.6.1.0. Using 1-sided alpha of 0.025, with

continuity correction, sample size of 40 per group (80 total) have 80.8% power (beta 0.192) to detect the difference of 95.7% in active arm vs 70% in control arm.

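### The SAP's MMRM names only a random subject effect and no residual covariance; run literally it is compound symmetry, and day-specific standard errors are then wrong if variances differ by day

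*SAP*

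**What the plan says.** SAP 9.2.3 (percent change in CRP, relative change in PaO2/FiO2) and SAP 9.3 (lymphocytes, ferritin, VEGF-A, cytokines) use the same model. The terms are group, study day, baseline, day-by-group and, to close the list, "interaction between study day and baseline, and subject as a random effect". Both sections label the model an MMRM. The protocol's counterpart, section 9.4.6, likewise has "group-by-study day interaction with subject as a random effect", and Protocol 9.4.4 has the same random effect for continuous safety data.

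Neither document states a residual covariance structure, a fallback if the model does not converge, a robust variance or a degrees-of-freedom method. SAP 1.0 says that the SAP overrides the protocol's outline of the analysis, so the protocol would not repair the gap even if it were fuller.

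Two other statements bear on this. Protocol 9.1 sets the error rate: "All tests of significance will be assessed at alpha level=0.05, 2-sided". SAP 7.3 leaves missing values unimputed and justifies this by the MMRM's small bias and nominal Type I error control when data are missing completely at random or at random, and to some extent beyond that.

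**The concern.** A random subject intercept with independent residuals gives every visit the same variance and every pair of visits the same correlation. The endpoints, however, are listed by individual day: CRP and most biomarkers at Days 3, 5, 7, 10, 14 and 28, cytokines at five of these. If variability changes over the four weeks, a comparison at a single day borrows a variance averaged over all days. Intervals are then too narrow on some days and too wide on others, so false positives rise at one end and power is lost at the other.

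The nominal error control invoked in SAP 7.3 depends on an adequate covariance model. That matters here because samples are scheduled only while the subject is in hospital, at discharge or early termination, and at Day 28. Gaps at the middle visits are built in, and with incomplete data the covariance influences the estimates as well as their standard errors.

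**Working it through.** **Inputs.** From the documents: 40 subjects per arm (SAP 5.0), two-sided alpha 0.05 (Protocol 9.1), six visits for CRP (SAP 9.2.3), model terms as above. Not in the documents, so assumed: the SDs by day, taken as linear over the six visits with a largest-to-smallest ratio of 1, 1.2, 1.5, 2 or 3.

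**The plan's own figure.** There is none for the MMRM. The stated sample size, for the primary endpoint, does reproduce. With 0.957 against 0.70, difference 0.257 and mean 0.8285:

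n' = [1.96·√(2·0.8285·0.1715) + 0.8416·√(0.957·0.043 + 0.70·0.30)]² / 0.257² = 32.6, or 33 per group.

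With continuity correction, n = (n'/4)·[1 + √(1 + 4/(n'·0.257))]² = 40 per group, as stated. This confirms the 40 per arm and has no bearing on the covariance question.

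**Step 1: what the literal model implies.** With random-intercept variance s_b² and residual variance s_e², Var(Y_t) = s_b² + s_e² at every day, and Corr(Y_t, Y_u) = s_b²/(s_b² + s_e²) for every pair of days.

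**Step 2: effect on a day-specific comparison.** With complete data and both day-by-group and day-by-baseline terms, the estimated group difference at each day is the same under any covariance. Only its standard error changes:

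model SE / true SE at day t = √(mean of SD² over visits) / SD_t = R_t

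rejection rate under no effect = 2·[1 − Φ(1.96·R_t)]

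Here SD_t is the SD after baseline adjustment.

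**Step 3: numbers.** For a 2-fold spread the SDs are 1, 1.2, 1.4, 1.6, 1.8 and 2. The mean square is 14.2/6 = 2.367, with root 1.538. At the most variable visit R = 1.538/2 = 0.77 and the rejection rate is 2·[1 − Φ(1.508)] = 13.2%. At the least variable, R = 1.54 and the rate is 0.3%.

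| SD ratio, largest to smallest | Root mean square SD | Most variable visit: R, rejection | Least variable visit: R, rejection |
|---|---|---|---|
| 1 (equal) | 1.000 | 1.00, 5.0% | 1.00, 5.0% |
| 1.2 | 1.102 | 0.92, 7.2% | 1.10, 3.1% |
| 1.5 | 1.262 | 0.84, 9.9% | 1.26, 1.3% |
| 2 | 1.538 | 0.77, 13.2% | 1.54, 0.3% |
| 3 | 2.113 | 0.70, 16.7% | 2.11, <0.1% |

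If SDs rise over time, the most variable visit is Day 28. If they fall, it is Day 3 and the pattern reverses.

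**Step 4: simulation check.** 40 per arm, six visits, no true effect, AR(1) correlation 0.7 between adjacent visits (assumed), 800 trials per setting, z tests; Monte Carlo SE about 0.8 points at 5%.

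- Random intercept, SD rising 2-fold, complete data: 0.2% at Day 3 and 12.1% at Day 28, in line with Step 3.
- Same, with assumed dropout depending on the previous value: 0.5% at Day 3 and 16.0% at Day 28 (R = 0.72).
- Random intercept, equal SDs: 4.2% to 5.1% with complete data and 4.4% to 6.1% with dropout, although the true correlation was not constant. Unequal variance, not the correlation pattern, drives the error.
- Unstructured covariance, SD changing 2-fold in either direction: 4.2% to 7.9% across days, against 0.0% to 16.0% for the random intercept.

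**Step 5: day-averaged contrast.** With complete data, compound symmetry preserves the average variance and the average covariance. The variance of the mean over visits depends only on these, so the standard error of a day-averaged group difference remains right.

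**The case against.** The strongest reply is that this is an omission and not a wrong choice. A reader might infer that the SAP commits the analysis to one variance and one correlation. It does not say so: it lists model terms under the label MMRM, which many programmers would implement with an unstructured residual matrix, and nothing excludes that. This stands. What remains is that the only structure actually written down is the random intercept, and that two programmers following the SAP could report different p-values.

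Second, the harm is conditional. A reader might infer that the planned intervals are wrong, or that Day 28 in particular is prone to false positives. The documents give no SD for any day, so neither the size nor the direction over time can be established; with equal variances there is no problem. This stands too.

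Third, SAP 9.2.3 promises an assessment of treatment differences without saying in so many words that each day is tested. For a day-averaged difference with complete data the literal model is adequate. But endpoints listed by day and a day-by-group interaction point to day-specific comparisons.

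Fourth, it is tempting to extend the point to every repeated measure. The SAP does not support that: clinical status (9.2.2), laboratory data (10.2) and vital signs (10.4) are descriptive only, and the number-of-days endpoints use ANOVA. PaO2/FiO2 runs only to Day 5, so the six-visit figures do not describe it.

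Finally, an unstructured matrix may fail to converge with 40 per arm and samples lost after discharge, and with z tests it still rejected up to 7.9%. That is a reason for a fallback order and a small-sample method, not for the random intercept.

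**Conclusion.** The point holds as a specification gap whose literal reading is compound symmetry. Under that reading, day-specific tests at the most variable visit run between 5.0% and 16.7% over the range from equal to 3-fold SDs, with a corresponding loss of power at the least variable visit. These figures assume linear SDs over six visits, complete data and normal-theory tests; they illustrate the range and do not predict what this trial will show.

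The consequences are confined to two secondary endpoints (CRP and PaO2/FiO2) and the exploratory biomarkers. The change is worth making before unblinding, because it is valid whether or not the variances are equal and because a structure chosen afterwards would be a post-hoc decision. It does not threaten the trial's main conclusion.

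**What to change.** In SAP 9.2.3 and 9.3, delete the random subject effect and state instead:

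- within-subject dependence across study days is modelled by an unstructured residual covariance (in SAS, a REPEATED statement), fitted by REML;
- degrees of freedom are by Kenward-Roger;
- if the model does not converge, the order is heterogeneous Toeplitz, then heterogeneous compound symmetry, and the structure used is reported;
- whether the group comparison is made at each listed day, averaged over days, or both.

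The random intercept should be replaced and not kept alongside, since its variance cannot be separated from an unstructured matrix.

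The cost is a few lines of SAP text and one SAS statement. The downside is small: 6·7/2 = 21 covariance parameters for six visits (5·6/2 = 15 for the five cytokine days) and possible non-convergence, which the fallback order covers. No change is needed to data collection, sample size, the primary analysis or the futility rule.

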3.2.2. Secondary Endpoints

- Types, frequencies, and severities of AEs and the relationships of AEs to IP; includes serious adverse events SAEs
- Proportion of subjects alive and free of respiratory failure at Day 60
- Change in clinical status (on a 0-8-point ordinal scale²) of subject at Day 7, Day 14, and Day 28
- Proportion of subjects alive and discharged from ICU at Days 14 and 28

² 8-category ordinal scale of patient health status ranges: 0=no clinical or virological evidence of infection; 1=no limitation of activities; 2=limitation of activities; 3=hospitalized, no oxygen therapy; 4=oxygen by mask or nasal prongs; 5=non-invasive ventilation or high-flow oxygen; 6=intubation and mechanical ventilation; 7=ventilation + additional organ support – pressors, rapid response team (RRT), extracorporeal membrane oxygenation (ECMO); 8=death.

- Time from randomization to first occurrence of respiratory failure or death on study due to any cause up to Day 28
- Percent change from baseline in CRP at Days 3, 5, 7, 10, 14, 28
- Relative change from baseline in oxygenation index (PaO₂/FiO₂) up to Day 5
- All-cause mortality at Day 60 and Day 90
- Number of days alive and free of respiratory failure at Day 28
- Number of days with respiratory failure up to Day 28
- Number of days hospitalized up to Day 28
- Number of days in ICU (length of stay) up to Day 90
- Number of days alive outside of hospital up to Day 28
- Number of days alive outside of hospital up to Day 90
- To assess the pharmacokinetic profile in the study population

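### Three secondary day counts are tested by ANOVA with no rule for subjects who die, so an early death can score as a short stay

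*SAP*

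**What the plan says.** SAP 9.2.3 (Continuous Endpoints) gives one method for all six day counts: "Treatment differences between groups will be assessed using analysis of variance (ANOVA) model with group as a fixed effect". Under SAP 6.1 efficacy is analysed in all randomized subjects.

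Three of the six counts build survival into the definition, for example "Number of days alive outside of hospital up to Day 90". The other three do not:

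- "Number of days with respiratory failure up to Day 28"
- "Number of days hospitalized up to Day 28" (Protocol 3.2.2, repeated in SAP 9.2.3)
- "Number of days in intensive care unit (ICU) (length of stay) up to Day 90"

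The general rules in SAP 7.3 do not supply a value for death:

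- "Missing values will not be imputed unless otherwise specified", and nothing is specified for these counts.
- "For success/failure endpoints, subjects who discontinue prior to the specified time point will be included in the analysis as treatment failures" covers binary endpoints only.
- "For all other endpoints, the mixed effect model repeat measurement (MMRM) analysis will be employed" does not fit a single count per subject and disagrees with the ANOVA in 9.2.3.

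Protocol 9.4.5 and 9.4.6 add no death rule. All-cause mortality is a separate endpoint in SAP 9.2.1.

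**The concern.** On these three counts fewer days is meant to be better. A subject who dies in hospital on Day 3 would contribute 3 hospital days; a subject who leaves hospital after 12 days contributes 12. The trial's own ordinal scale (Protocol 8.1.9) puts death last, at score 8, yet here an early death takes one of the best values.

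Deaths within the window are foreseeable. The population has severe COVID-19, and SAP 5.0 assumes that 30% of placebo subjects will be dead or in respiratory failure at Day 28. The difference in means therefore mixes faster recovery with faster death. Three tested comparisons could hide a mortality difference or point against the mortality and alive-based results from the same subjects. The distortion also works in reverse: a drug that prevents early deaths would be charged with the bed-days of the subjects it saved.

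**Working it through.** **The plan's own figure.** The documents give no figure for these counts. The only input taken from them is the arm size. For 95.7% v 70%, two-sided 0.05 and 80% power, the two-proportion formula gives 33 per group, and 40 with continuity correction. The planned 40 per group is reproduced.

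**Hospital days: formula.** Assumed, because the documents do not give them: survivors' mean stay s = 11 days, the same in both arms; all deaths in hospital, with mean death day d the same in both arms; mortality 10% on placebo (pP) and 20% or 30% on drug (pD).

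The mean count in an arm with mortality p is p·d + (1 − p)·s, so

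drug minus placebo = (pD − pP) × (d − s).

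If deaths are scored 28, d is replaced by 28.

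- d = 4: 0.10 × (4 − 11) = −0.7; 0.20 × (4 − 11) = −1.4
- d = 7: 0.10 × (7 − 11) = −0.4; 0.20 × (7 − 11) = −0.8
- d = 11: zero at either mortality
- d = 18: 0.10 × 7 = +0.7; 0.20 × 7 = +1.4. Capping at Day 28 lowers these to about +0.6 and +1.2 in simulation.
- deaths scored 28: 0.10 × (28 − 11) = +1.7; 0.20 × 17 = +3.4

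**Hospital days: significance.** Simulated with 40 per arm, stays and death days drawn from gamma distributions (shape 4), rounded and capped to 1–28. Two-group ANOVA is the pooled t-test on 78 df. With equal mortality, a significant result favours the drug in about 2.5% of trials.

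| Deaths around | Difference, drug − placebo (20% / 30% mortality) | Significant in favour of drug |
|---|---|---|
| Day 4 | −0.7 / −1.4 days | about 8% / 20% |
| Day 7 | −0.4 / −0.8 days | about 5% / 10% |
| Day 11 | about 0 / 0 | about 2.5% / 2.5% |
| Day 18 | +0.6 / +1.2 days | below 2.5% |

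**Respiratory-failure and ICU days.** A separate illustration. Assumed: a subject who dies on day d has d − 2 respiratory-failure days and d − 1 ICU days; a survivor with respiratory failure averages 14 and 16; everyone else has none. Deaths average Day 12 in both arms, and mortality is 30% on drug v 15% on placebo.

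- *Extra deaths replace long survivor stays* (15% of placebo subjects and no drug subjects survive respiratory failure). Respiratory-failure days: 0.30 × 10 = 3.0 v 0.15 × 10 + 0.15 × 14 = 3.6. ICU days: 0.30 × 11 = 3.3 v 0.15 × 11 + 0.15 × 16 = 4.05. Both favour the drug with twice the mortality. In simulation (6,000 trials) each is significant in its favour in about 6% of trials.
- *Extra deaths fall on subjects who would otherwise have had no respiratory failure* (15% survive respiratory failure in both arms). Respiratory-failure days: 3.0 + 0.15 × 14 = 5.1 v 3.6. ICU days: 3.3 + 0.15 × 16 = 5.7 v 4.05. The drug now looks worse, and a significant result in its favour occurs in about 0.2% of trials.

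The extreme case in that simulation (30% mortality around Day 5 on drug v 15% around Day 18 on placebo) gave significant results for the harmful drug in 83% to 91% of trials across the three counts. It requires deaths to be both commoner and much earlier on drug, so it is an upper end and not an expectation.

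**The case against.** **Nothing in the SAP says that counting stops at death.** This is correct. A reader might infer that the plan prescribes it, but the documents are silent. It is the literal consequence of counting hospital, ICU or respiratory-failure days. The alternative, treating deaths as missing under the no-imputation rule, produces a different bias but does not penalise death either. What can be stated firmly is that no death rule exists.

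**The reversal is not inevitable.** A reader might infer that a harmful drug will look beneficial. The documents do not support that, because they give neither mortality nor its timing. The sign turns on whether deaths come before or after the average discharge, and on which subjects die. The share of trials whose estimate merely leans towards the drug (about 71% and 86% with Day 4 deaths) must not be read as an error rate: no effect would give about 50%, and significant results are far rarer.

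**Neighbouring endpoints already cover death.** This largely stands. For subjects who die in hospital, scoring death as 28 hospital days is exactly 28 minus the planned days alive outside hospital to Day 28, so recoding the hospital count adds little. Respiratory-failure days has a close counterpart in days alive and free of respiratory failure. ICU days to Day 90 has no alive-based day count, only the proportion alive and discharged from ICU at Days 14 and 28.

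**The consequence is limited.** This also stands. The primary endpoint counts death as failure, mortality at Days 60 and 90 is tested, time to respiratory failure or death has a log-rank test, and the futility look uses the primary endpoint only.

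**Conclusion.** The concern holds as a flaw in three secondary comparisons. Each is tested with no alive condition and no value for death, so the difference in means does not have a dependable direction when mortality differs between arms.

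Under the stated assumptions, a doubling or tripling of mortality moves the hospital-day difference anywhere from 1.4 days in favour of the drug to 1.2 days against it, depending only on whether deaths cluster near Day 4 or Day 18. Near Day 11 the harm disappears from the endpoint altogether. Scoring deaths 28 would show 1.7 or 3.4 days of harm throughout. These sizes rest on assumed mortality, timing and stay.

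The trial's main conclusion is not at risk. The practical weight falls chiefly on ICU days, then on respiratory-failure days. The change should be made, but the trial does not depend on it.

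**What to change.** In SAP 9.2.3, before unblinding:

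1. For ICU days (horizon Day 90) and respiratory-failure days (horizon Day 28), rank every subject who dies before the horizon as worst and compare arms with a Wilcoxon rank-sum test in place of ANOVA.
2. Report days hospitalized descriptively, and use the planned days-alive-outside-hospital endpoints for the hospital-stay comparison.
3. Show the raw counts of all three endpoints, split by survivors and deaths, beside mortality.
4. Reconcile the MMRM sentence in SAP 7.3 with the method in 9.2.3, since each subject contributes one count.

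Making all three counts descriptive beside mortality would also be defensible.

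The cost is a few sentences. Survival, hospital and ICU stays are already collected to Day 90 (Protocol 8.1.12 and 8.2.5 to 8.2.7). The small downside is that the tested quantity is no longer literal bed-days, which is why the raw counts stay in the tables. The power of the rank test was not evaluated here.
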